8.4 Data Presentation Conventions

Continuous safety variables (e.g., clinical laboratory values and vital signs) will be listed to the same precision as the source data. Derived variables will be calculated and listed using the same precision as the value(s) from which they were derived.

For the tabular reporting of descriptive statistics:

- Continuous variables: the same number of decimal places as in the raw data will be presented when reporting minimum and maximum, 1 more decimal place than in the raw data will be presented when reporting mean and median, and 2 more decimal places than in the raw data will be presented when reporting SD.
- Categorical/discrete variables: the frequency count and the percentage (of available data) for each class of the variable will be presented and will be displayed in the form XX (XX.X%) where the percentage is in the parentheses. All percentages will be presented to 1 decimal place, unless otherwise specified. Percentages equal to 100

will be reported as 100% and percentages will not be presented for zero frequencies.

Unless otherwise specified, percentages will be calculated based on the number of patients specified by the appropriate population definition.

- Date variables: formatted as DDMMYY for presentation. Time will be formatted in military time as HH:MM for presentation.

Extra measurements (such as unscheduled or repeat assessments) will not be included in summary tables but will be included in patient listings. They will be used in summary tables which are not ‘time specific’, for example, summaries of maximum post dose values.

All tables, listings, figures will be produced in landscape orientation using Times New Roman 9-point font. Output files will be created in rich text file (RTF) format.

Missing or invalid data will be generally treated as missing, not imputed, unless otherwise stated (see Section 9.5).

The table, figures and listing shells and table of contents as part of this SAP provide the expected layout and titles of the tables, listings and figures. Any changes to format, layout, titles, numbering, or any other minor deviation will not necessitate a revision to the SAP nor will it be considered a deviation from planned analyses. Only true differences in the analysis methods or data handling will necessitate such documentation. The appropriate listings supporting the tables will be included and are not specified in the individual sections throughout the document.

Minor modifications may be necessary to the planned design of tables, listings and figures to accommodate data collected during the actual study conduct. Any major deviations from the final approved SAP (e.g., change in the population used, change from statistical method/assumption listed, transformation of data type [e.g., continuous data transformed to categorical], exclusion of planned analysis, etc.) or additional unplanned analyses will be documented (with justification) in the CSR.

8.5 Treatment Comparisons

The following labels for dose level will be used on all tabulations, in the following order:

Lead-In Cohort			Stage 1			
Arm 1: ALDAC (N=3)	Arm 2: ALV (N=4)	Total (N=7)	Arm 1: ALDAC (N=2)	Arm 2: ALV (N=2)	Total (N=4)	Overall (N=11)

8.6 Definitions, Computations, Derived Data

- Screening: Screening is defined as \leq 14 days prior to Cycle 1 Day 1 prior to the first study drug administration.
- Baseline: Measurements taken at Screening or prior to receiving the first dose of study drug; whichever is latest.
- 1 year = 365.25 days. Year is calculated as (days / 365.25) and will be rounded to 1 digit after the decimal point (tenths) for presentation purposes.
- 1 month = 30.4375 days. Month is calculated as (days / 30.4375) and will be rounded to 1 digit after the decimal point (tenths) for presentation purposes.
- 1 pound = 0.454 kg and 1 kg = 2.2 pounds.
- 1 inch = 2.54 cm and 1 cm = 0.3937 inches.
- Body mass index (BMI) calculated as [weight (lbs) / height (in)²] x 703.
- Age will be calculated in years relative to the date of study consent based on the following SAS statement: Age = ([Consent Date - Date of Birth] / 365.25) and will be rounded to 1 digit after the decimal point (tenths) for presentation purposes.

9. GENERAL CONSIDERATIONS FOR DATA ANALYSES

The listings, figures and summary tables for the disposition and safety, and efficacy data will be the responsibility of the study Biostatistician at Vantage Data Designs.

The currently supported version of SAS software (9.4 or later) will be used to perform all data analyses. The actual SAS version used will be presented in the Clinical Study Report.

All data in the database will be presented in the data listings. Unless otherwise stated, all listings will be sorted by cohort (lead-in, stage 1), patient number and assessment date/time.

Unless otherwise stated, continuous variables will be summarized using descriptive statistics including number of non-missing observations, mean, standard deviation, median, minimum and maximum values. Categorical variables will be summarized with frequency counts and percentages. The population size (N for sample size and n for available data) and the percentage (of available data) for each class of the variable will be presented.

9.1 Multicenter Studies

Data from all participating sites will be pooled for the analysis.

9.2 Other Strata and Covariates

Not applicable for this study.

9.3 Examination of Subgroups

Not applicable for this study.

9.4 Multiple Comparisons and Multiplicity

Not applicable for this study.

9.5 Missing Data and Dropouts

The issue of how to handle missing data caused by dropouts in clinical studies is a research topic that is still under development in the statistical literature. As has been noted in the ICH-E9 guideline, “no universally applicable method of handling missing values can be recommended”. The best approach is to minimize the chance of dropouts at the design stage of the clinical study and during study monitoring.

In general, data will be analyzed as received from the clinical database. Hence, missing values will not be replaced by imputed values.

9.5.1 Adverse Events

Adverse events with missing or partial dates will be handled such that in the absence of contradictory information an AE is classified as “treatment emergent”.

9.5.2 Concomitant Medications

Medications with missing or partial dates will not have dates imputed and will be presented as collected in the patient listings.

9.5.3 Other Situations

For patients who are withdrawn from the study prior to study completion, all data compiled up to the point of discontinuation will be used for analysis. All withdrawals will be included in all analyses up to the time of withdrawal.

10. STUDY POPULATION

All disposition, baseline and demographic analyses will be conducted on the Safety population.

10.1 Patient Disposition

The patient disposition summary will include:

- The number of patients who were enrolled at each study center.
- Number of patients in Lead-In Cohort and Stage 1.
- A summary of primary reason for treatment discontinuation from study.
- A summary of primary reason for discontinuation from study.

A listing of patient enrollment and disposition will be provided. A listing of whether or not all inclusion and exclusion criteria were met and if not, which criteria were not met, by patient, will also be presented.

10.2 Protocol Violations or Deviations

Protocol deviations were not collected per the eCRFs.

10.3 Demographics

Demographic characteristics will include age, age category (18-25, 26-35, 36-45, 46-55, 56-65, >65 years), sex, race, ethnicity, and ECOG Performance Status.

The categorical (discrete) variables will be summarized using counts and percentages. The continuous variables will be summarized using mean, median, standard deviation, and range (maximum, minimum). All demographic data will be listed by patient.

10.4 AML History

AML History variables include French-American-British (FAB) AML Type, MDS prior to AML, Primary or Secondary AML, Extramedullary Disease, central nervous system (CNS) involvement, FLT3 Mutations, CEBPA (C/EBP-Alpha) Mutations, NPM1 Mutations, ASXL1 Mutations, and RUNX1 Mutations.

The categorical (discrete) variables will be summarized using counts and percentages. The continuous variables will be summarized using mean, median, standard deviation, and range (maximum, minimum). All AML history data will be listed by patient.

10.5 Medical History

The incidence of Medical history will be summarized by system organ class (SOC) and preferred term (PT) using MedDRA version 21.1. In the summary tables, patients may be counted under multiple system organ class (SOC) and preferred terms (PT), but for each SOC and PT category, patients will be counted only once. All medical history data will be presented in patient listings.

10.6 Concomitant Medications

All prior medication and concomitant medications will be presented in patient listings.

10.7 Study Drug Administration and Exposure

Study drug administration and exposure will be summarized by number of treatment cycles completed and the number of weeks on study. The categorical (discrete) variables will be summarized using counts and percentages. The continuous variables will be summarized using mean, median, standard deviation, and range (maximum, minimum). All study drug administration data will be listed by patient.

11. EFFICACY ANALYSIS

The response criteria for this study are from the 2017 European Leukemianet recommendations from an international expert panel (Blood 2017;129(4):424–447).

Response categories include CR, CR_i, CR_h, CR_{MRD}, MLFS, PR, SD, PD, Not Evaluated / Missing. The best objective response for each patient will be summarized by number and percentage.

In addition, response rates will be categorized and summarized by number and percentage of patients meeting these definitions:

- Combined Complete Remissions (CR, CR_i).
- Composite Complete Remission Rate (CR, CR_i, CR_h).
- Combined Response Rate (CR, CR_i, CR_h, MLFS, and PR).

In addition to the summary tables, efficacy data will also be presented in the individual patient listings.

12. SAFETY ANALYSIS

The Safety Population is defined as all enrolled patients who received any amount of study treatment will be utilized for all safety analyses.

In addition to the summary tables, safety data will also be presented in the individual patient listings.

12.1 Treatment Emergent Adverse Events

Treatment-emergent adverse events (TEAEs) are defined as all AEs that begin on or after the date of the first administration of study drug. Related AEs are those reported as possibly related, probably related, or related to study drug (ALDAC or ALV). The verbatim terms of

the Treatment Emergent Adverse Events (TEAE) will be coded to preferred terms (PT) and system organ classes (SOC) per MedDRA® (Medical Dictionary for Regulatory Activities) Version 21.1 (or later).

All reported AEs (including non-TEAEs) will be listed, documenting all information collected on the eCRF including verbatim term, MedDRA preferred term, MedDRA system organ class, start date, stop date, severity and relationship to study drug action taken, and outcome.

The TEAEs will be graded by the Investigator in terms of:

- Severity graded 1-5 according to CTCAE v5.0:
 - 1=Mild, 2=Moderate, 3=Severe, 4= Life Threatening, 5=Fatal.
- Relation to study drug (ALDAC or ALV):
 - 'Related' includes events where the causality was reported as 'Possibly Related', or 'Probably Related', or 'Definitely Related', or where the relationship was not reported on the eCRF.
 - 'Not Related' includes events where the study drug causality was reported as 'Unrelated' or 'Unlikely Related' on the eCRF.

All TEAE summary tables will be presented with the number and percentages of patients in the Safety population. An overall summary of TEAEs will be tabulated by treatment regimen, relation to study treatment, and grade. In addition, TEAEs will be summarized by system organ class (SOC) and preferred term (PT).

Planned TEAE summary tables include:

- Overall Summary of Treatment-Emergent Adverse Events (Safety Population)
- Incidence of Treatment-Emergent Adverse Events by MedDRA System Organ Class and Preferred Term (Safety Population)
- Incidence of Treatment-Emergent Adverse Events by MedDRA System Organ Class, Preferred Term, and CTCAE Severity Grade (Safety Population)
- Incidence of Treatment-Emergent Grade 3, Grade 4, and Grade 5 Adverse Events by MedDRA System Organ Class and Preferred Term (Safety Population)
- Incidence of Treatment-Emergent Grade 3, Grade 4, and Grade 5 Adverse Events by MedDRA System Organ Class and Preferred Term and CTCAE Severity Grade (Safety Population)

- Incidence of Treatment-Emergent Adverse Events Judged Possibly, Probably or Definitely Related to the Study Drug Regimen by MedDRA System Organ Class and Preferred Term (Safety Population)
- Incidence of Treatment-Emergent Grade 3, Grade 4, and Grade 5 Adverse Events Judged Possibly, Probably or Definitely Related to the Study Drug Regimen by MedDRA System Organ Class and Preferred Term (Safety Population)

In the summary tables, patients may be counted under multiple system organ class (SOC) and preferred terms (PT), but for each SOC and PT category, patients are only counted once. If a patient has the same AE on multiple occasions, the highest severity grade (fatal > life threatening > severe > moderate > mild) or drug relationship (related > possibly related > not related) recorded for the event will be summarized.

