	
treatment-emergent (TEAEs) will be summarized. A TEAE is an AE that starts or increases in severity any time after the first administration of any study drug up to 30 days following the last administration of any study drug. AE severity is rated by the Investigator according to CTCAE version 5.
 
A high-level safety summary will display the numbers of patients within each treatment arm and overall who experience one or more AEs in each of the following categories:
 
• All TEAEs regardless of severity or presumed relationship to study drug• TEAEs judged related to study drug• All TLS SMQ TEAEs• TLS SMQ TEAEs judged related to study drug• Treatment-emergent SAEs• TEAEs leading to a delay in the administration of study drug• TEAEs leading to a reduction in the protocol-specified dose of study drug• TEAEs leading to discontinuation of study drug• TEAEs leading to withdrawal from study treatment• TEAEs leading to death. 
The base summary of TEAEs will show within- and between-treatment-arm incidence rates for each MedDRA primary System Organ Class (SOC) and/or Preferred Term (PT) by highest reported CTCAE severity grade and overall. A separate summary will be produced each of the AE subsets listed above. Additional AE summaries may be produced using safety data from subsets of patients and/or characterized using additional SMQs.
 
PD Analyses
 
Summary of baseline biomarker values will include within- and between-treatment-arm descriptive statistics. If there are sufficient numbers of patients achieving remissions for an analysis to be informative, a logistic regression model will be fit to examine the relationship between potential biomarkers and the independent binary variables complete remissions, combined complete remissions, and combined remissions during the study.

--	---

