5.3 Cycles 2+

Patients who achieve CR, CRi, CRh, MLFS, PR, or clinical benefit after the first cycle (completion of all doses) may receive additional optional cycles of treatment until disease progression (in the event of toxicities see the recommendations in [Table 3](#), if applicable).

Those who achieve a CR, CRi, CRh, or MLFS (ie, <5% blasts in bone marrow) should not be given **subsequent cycles** until ANC >0.5 and platelets >50. If treatment is delayed >2 weeks for cytopenias, a bone marrow biopsy should be performed to reassess disease status.

Patients not demonstrating evidence of CR, CRi, CRh, MLFS, PR, or clinical benefit after 4 cycles of treatment will be considered for removal from the study, although with permission of the Medical Monitor, treatment may continue if clinically indicated (in the event of toxicities see the recommendations in [Table 3](#), if applicable).

There is a maximum limit of 6 weeks between the start of cycles unless otherwise discussed with the medical monitor.

5.3.1 Cycles 2+: At Least 2 Hours Prior to First Dose (± 3 days)

During Cycles 2+, pretreatment IV hydration, oral allopurinol, and oral phosphate binder may be discontinued if serum uric acid and phosphorus levels are within normal limits and there is no evidence of TLS.

Should TLS be suspected during subsequent cycles, perform the following procedures at least 2 hours prior to starting therapy on Day 1 (unless otherwise stated):

- Initiate supportive care measures prior to first dose in all patients to minimize the likelihood of TLS:
 - Administer pretreatment IV hydration and determine if oral allopurinol and oral phosphate binder are still clinically indicated (see [Section 4.5.1](#))

- Assess patient for adequate hydration at all study visits and replace excessive fluid losses, including from diarrhea, unless otherwise clinically indicated ([Section 4.5.1.2](#) and [Section 4.5.1.3](#))
- Review study diary and remind patient to bring diary back at next clinic visit

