5.4 End of Treatment Assessments

If, at any time, a patient discontinues study treatment, a visit should be scheduled as soon as possible and within 14 days of the last dose of study drug or within 14 days of the decision to discontinue study treatment. If the decision to withdraw the patient occurs at a regularly scheduled visit, that visit may become the End of Treatment visit rather than having the patient return for an additional visit.

- Abbreviated physical examination (AE- or symptom-directed exam) including weight (kg) and other measures of disease and disease symptoms, eg, extramedullary disease
- Vital signs (temperature, heart rate, systolic and diastolic blood pressures)
- ECOG PS ([Appendix B](#))
- 12-lead ECG only if clinically indicated
- Collect blood for evaluation of laboratory studies ([Appendix D](#)):
 - Hematology
 - Full serum chemistry panel

- Fibrinogen level (only required if clinically indicated)
- Record only those medications (prescription, nonprescription, nutritional supplements) administered in conjunction with an AE
- Urinalysis
- Collect bone marrow and peripheral blood samples (if not done within the previous 30 days):
 - Collect bone marrow and peripheral blood for response assessment, PD tests ([Section 7.3](#)), and treatment guidance.
 - Collect bone marrow sample to be sent to a central laboratory for MRD assessment using standardized techniques (ie, MPFC and molecular testing including NGS) ([Appendix D](#))
 - If the bone marrow procedure is nonproductive or not diagnostic, it must be repeated within 7-10 days. In addition, 6 to 8 bone marrow slides will be prepared and sent to the Sponsor. Details regarding the collection and shipping of these slides is provided in the Laboratory Manual.
- Assess for AEs
- Collect study diary

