11.4.3 Safety Analyses

The following safety analyses will be performed on all patients who receive at least one dose of study drug (***including patients in the safety lead-in cohort***).

Adverse Events

Reported AE terms will be mapped to MedDRA preferred terminology. Adverse events suggestive of TLS will be flagged based in the standardized MedDRA query (SMQ) for TLS. All reported events will appear in AE listings, however only treatment-emergent adverse events (TEAEs) will be summarized. A treatment-emergent adverse event is an AE that starts or increases in severity any time after the first administration of any study drug up to 30 days following the last administration of any study drug. Adverse event severity is rated by the Investigator according to Common Terminology Criteria for Adverse Events (CTCAE) version 5 criteria.

A high-level safety summary will display the numbers of patients within each treatment arm and overall who experience one or more AEs in each of the following categories:

- All TEAEs regardless of severity or presumed relationship to study drug
- TEAEs judged related to study drug
- All TLS SMQ TEAEs
- TLS SMQ TEAEs judged related to study drug
- Treatment-emergent serious adverse events (SAEs)
- TEAEs leading to a delay in the administration of study drug
- TEAEs leading to a reduction in the protocol-specified dose of study drug
- TEAEs leading to discontinuation of study drug
- TEAEs leading to withdrawal from study treatment
- TEAEs leading to death.

The base summary of TEAEs will show within- and between-treatment-arm incidence rates for each MedDRA primary System Organ Class (SOC) and/or Preferred Term (PT) by highest reported CTCAE severity grade and overall. A separate summary will be produced for each of the AE subsets listed above. Additional AE summaries may be produced using safety data from subsets of patients and/or characterized using additional SMQs.

Clinical Laboratory Assessments

Laboratory test results measured on a continuous scale and changes from baseline values will be summarized by visit and within alvocidib dose level using mean, standard deviation, median, minimum and maximum values. Categorical test results will be summarized within alvocidib dose level using shift tables. Additionally, for tests where NCI CTCAE, version 5.0, severity criteria are specified, NCI CTCAE severity grades will be summarized in shift tables.

Vital Signs

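### The only TLS SMQ table named in the SAP text is related-only although the protocol also requires an all-causality summary, and SAP 12.1 narrows and widens the TEAE definition without recording it

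*SAP*

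**What the plan says.** The protocol defines a TEAE twice, in the same terms. The synopsis has "A TEAE is an AE that starts or increases in severity any time after the first administration of any study drug" and goes on to the 30-day end of window. Section 11.4.3 has "starts or increases in severity any time after the first administration of any study drug up to 30 days following the last administration".

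Section 11.4.3 then lists the categories of a high-level safety summary. Two concern TLS: "All TLS SMQ TEAEs", and the subset judged related to study drug. It adds: "A separate summary will be produced for each of the AE subsets listed above".

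The SAP differs in three places.

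- Section 12.1: "Treatment-emergent adverse events (TEAEs) are defined as all AEs that begin on or after the date of the first administration of study drug". No other SAP section restores an end of window or a worsening rule. Section 9.5.1 deals only with missing or partial dates.
- Sections 12.1 and 12.2 name the planned TEAE tables. One uses the TLS SMQ. It is laid out by preferred term, limited to events rated possibly, probably or definitely related, and placed under the serious-event heading although its title does not say serious.
- Section 16, on changes from the protocol, gives the protocol version and a general statement that the SAP supersedes it. It lists no individual change.

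SAP 8.4 describes table shells as part of the SAP. They are not in the text available for this review.

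**The concern.** TLS is the risk around which much of this trial's safety management is built: mandatory hydration, allopurinol and phosphate binder, the exclusion of high blast counts, and repeated tumor lysis laboratory tests (protocol 2.8 and 4.5.1.1). The protocol asks for the all-causality count and the related count so that a reader sees both the whole and the attributed part. A table holding only the second leaves the number of patients with any TLS SMQ event unreported.

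The definition matters for a related reason. Enrolment stopped at 11 patients (3 + 4 in the lead-in cohort, 2 + 2 in Stage 1) and no inferential analysis is planned, so the report rests on descriptive tables and listings. A reader with the protocol in hand would assume that TEAE means what the protocol says, and the SAP section meant to disclose changes would not correct that assumption.

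**Working it through.** The plan gives no figure to reproduce here; the check is a comparison of texts, with one piece of timing arithmetic.

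**1. TLS summaries.** Let A be the number of patients with any TLS SMQ TEAE, and R the number with at least one rated related. The protocol asks for both. R cannot exceed A, and A − R is the number of patients whose TLS SMQ events were all rated unrelated or unlikely. SAP 12.1 classes unreported causality as related, so those events stay in R. The SAP text names a table for R only.

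Can A be read from the all-causality SOC and preferred-term tables? SAP 12.1 counts a patient once per preferred term but allows the same patient under several terms. If nᵢ is the count for the i-th TLS SMQ term and N the column size, those tables give only

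max(nᵢ) ≤ A ≤ min(N, Σnᵢ).

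For illustration, two TLS terms with one patient each give A = 1 if it is the same patient and A = 2 if not. A would have to be rebuilt from the listings.

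**2. TEAE definitions side by side.**

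| Element | Protocol synopsis and 11.4.3 | SAP 12.1 |
|---|---|---|
| Onset after first dose | counts | counts |
| Worsening after first dose | counts | not mentioned |
| End of window | 30 days after last dose | none |

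**3. Direction of the missing end of window.** An AE starting from first dose to 30 days after last dose meets both rules. One starting later meets only the SAP rule. The change can add events to the TEAE tables and cannot remove any.

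When could a visit fall past 30 days? Inputs:

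- The last dose of a cycle is on Day 15, window Day 13 to 17 (protocol 5.2.3 and 5.3.3).
- Protocol 5.3: "There is a maximum limit of 6 weeks between the start of cycles unless otherwise discussed with the medical monitor". The latest next start is Day 1 + 42 = Day 43.
- Protocol 5.4 places the End of Treatment visit "within 14 days of the last dose of study drug or within 14 days of the decision to discontinue study treatment", and if the decision is made at a scheduled visit, "that visit may become the End of Treatment visit rather than having the patient return for an additional visit".

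Interval = visit day − day of last dose:

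- Delayed to Day 43, and that visit serves as End of Treatment: 43 − 15 = 28 days (43 − 17 = 26 to 43 − 13 = 30). This is inside the limit.
- Delayed to Day 43, full 14 days used (Day 57): 57 − 15 = 42 days (57 − 17 = 40 to 57 − 13 = 44). This is 10 to 14 days past the limit.
- Decision on Day 28: 28 − 15 = 13 days (latest 31 − 13 = 18).
- Decision on Day 28, full 14 days used: 42 − 15 = 27 days (latest 45 − 13 = 32).

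So scheduled visits reach beyond 30 days mainly when a long delay ends in discontinuation and the whole visit allowance is used. After the last scheduled visit, protocol 8.6 still calls for reporting of events judged reasonably drug-associated or otherwise reportable.

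**4. The missing worsening criterion.** A loss needs an AE recorded with onset before first dose that worsens afterwards without a new entry. Protocol 8.4 captures AEs from first dose and dates reportable laboratory AEs at their highest grade. SAP 9.5.1 treats an AE with a missing or partial date as treatment emergent unless something contradicts it. The route is therefore narrow.

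**The case against.** The strongest reply is that nothing is hidden. Protocol section 11 calls itself an overview and leaves detail to the SAP. The SAP states its definition openly and says it supersedes the protocol, so nobody is unsure which rule applies. Section 16 itemizes no change of any kind, so the silence is not peculiar to TEAEs. An open-ended window is inclusive and defensible, and restoring the limit would take events out of the tables. For TLS, the protocol's all-causality entry is a category of the high-level summary. The SAP keeps an overall TEAE summary whose layout is in shells not seen here, and its description need not be a full list of rows. SOC and preferred-term tables of any causality, plus listings of all AEs for 11 patients, still display every TLS term.

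Most of this stands. The governing definition is clear, the open window loses nothing, and the shells may already hold the row. Two things remain. The SAP text as it stands names no all-causality TLS SMQ summary, which the protocol requires, and the preferred-term tables cannot supply the patient count. Supersession settles which definition applies; it does not tell the reader that the definition changed.

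**Conclusion.** The point holds and is minor. Its main part is the TLS SMQ summary: on the SAP text alone, patients whose TLS SMQ events were all rated unrelated or unlikely are missing from the SMQ count. This is conditional on the shells. The definition change is real and unrecorded, but it mostly adds late events and has only a narrow route to losing one. How many events are affected cannot be computed from the documents, and no affected patient is shown. The timing figures assume that the Day 15 dose is given and the 6-week limit is kept; the interval is longer otherwise.

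A reader might infer more, and the documents do not support it:

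- That TLS events are concealed. All AEs, including non-TEAEs, are listed, and TLS terms of any causality appear in the SOC and preferred-term tables.
- That the related-only table contradicts the dose-limiting-toxicity rule, which ignores attribution. That rule is a Cycle 1 tolerability rule for the lead-in cohort, its TLS item carries a qualifier about resolution within 14 days, and it does not govern the final tables.
- That open-label attribution biases the count. Both arms receive alvocidib, and no such bias is shown.
- That one late event would swing a small column sharply. It moves an incidence cell only if it is that patient's first event in the cell, or a severity table only if it raises the maximum grade.

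**What to change.** 1. Check the table shells. Unless they already contain it, add an all-causality TLS SMQ TEAE summary showing the number of patients with at least one such event, beside the related-only one. A row in the Overall Summary of TEAEs would do.
2. Replace the first sentence of SAP 12.1 with the protocol rule: onset or increase in severity after first administration of any study drug, up to 30 days after the last administration. Keep later events in the listings. With the protocol rule restored, section 16 has no TEAE change left to record.

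The cost is one SAP sentence and at most one extra row or table, from data already collected. The downside is that events starting more than 30 days after last dose move from the TEAE tables to the listings. The SAP is to be finalized before database lock, which is the natural time to make both changes.
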